This study will be conducted in four sectors (Rwinkwavu, Murama, Ruramira, and Mwiri) of Kayonza district in eastern Rwanda. There are 9 [Migera, Gihinga, Nyarunazi, Gahengeli, Gashushyi, Rutonde, Raveri, Bugambira, Rukira] mining sites in Rwinkwavu, Murama, Ruramira and Mwiri, and all mining activities in these sites are supervised by Wolfram Mining and Processing LTD. All these sectors are located in the Rwinkwavu District Hospital catchment area.

[figure not shown]
Study design:

This will be a combination of a cross-sectional study to determine the prevalence of silicosis and a pre- and post-design to assess the silicosis-related knowledge, attitudes and practices (KAP) among mining workers before and after the implementation of a health education program.

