controls and personal safety assessment and deployment of the screening questionnaire. Silicosis related KAP data will be collected by skilled data collectors after a two week training program.

KAP: knowledge, attitudes and practices

Study population:

All eligible mine workers in Kayonza District in four sectors including: Rwinkwavu, Murama, Ruramira, and Mwiri sectors, located in the Rwinkwavu DH catchment area will be included in the study. Those miners with potential risk for RCS exposure, including those who handle mining either underground or above ground will be included. People who work in WOLFRAM administration (office) and never directly touch mines will not be included.

Study sample:

For the aim to determine the prevalence of silicosis, we used the single population proportion formula to calculate the required sample size. With the existing literature that silicosis prevalence among high-risk populations in LMICs may range between 30-50% [Trapido, A.S. *et al* (1998) Prevalence of occupational lung disease in a random sample of former mineworkers, Libode District, Eastern Cape Province, South Africa. American Journal of Industrial Medicine, Antão VC, Pinheiro GA, et al., High prevalence of silicosis among stone carvers in Brazil. Am J Ind Med. 2004], we used the most conservative estimate of 50% for a maximum sample size, with a level of confidence of 95%, 0.8 power and a level of precision of +/- 10% - a sample of 189 individuals will be required. For the silicosis-related KAP part of this study, we also used the most conservative estimate of 50%, a 95% confidence level, and a 0.8 power to detect a 20% difference from pre- to post-intervention. This gave us a required total sample size of 186 individuals (a minimum sample of 93 individuals will be required for the pre- and post-survey),

however the required sample size would increase to 224 individuals (112 individuals in each survey) after accounting for a 20% non-response rate. We estimate our study sample to be around 995 mine workers, so we will have ample participants to conduct our study. Our goal is to sample the complete mining population so as to obtain accurate prevalence of the full cohort of miners within the RDH catchment area, which may also allow us to detect asymptomatic disease in certain miners, and to enroll these patients in future surveillance programs

Recruitment of study participants and consent to participate

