Participants will be recruited from the mining and processing company Wolfram Mining and Processing Ltd., which operates in Rwinkwavu, Murama, Mwili, and Rurambira sectors. Inclusion criteria for all three study objectives, including silicosis screening, KAP assessment and education programs are: adult residents of Kayonza District aged 18 years or older who regularly (at least once per week) works in direct physical proximity with mining products in operations managed by Wolfram Ltd. at the present time or those who regularly worked in such mining operations for at least one cumulative year within the last 10 years. Exclusion criteria include those who have a significant impairment in speech or hearing due to the limited availability of adequate accessibility provisions for such study subjects, or other physical or medical disability that may limit involvement. Patients who are illiterate may still participate in the study with help from data collectors who can help study candidates complete forms and assessments. Recruitment procedures will be proposed to the managers of Wolfram Ltd. and finalized through consensus. We will propose that those who meet inclusion criteria be informed of the opportunity to receive a free medical screening and important information on staying healthy while working in the mining industry. Mine workers who accept to be a part of study, will avail him/herself two half days. Workers are in the mine in two possible shifts, typical shifts are from 6am-2pm (One site has a night shift from 4pm-early am). We plan to perform screening and education from 2-4pm at each site for workers who agree to participate so that all miners have access to the program. All relevant ethical information, including the risks and benefits of study participation will be provided to each prospective study subject in an informed consent document that will be made available in written and oral form in both Kinyarwanda and English.

Data collection

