Questionnaire data will be collected by trained data collectors and supervised by faculty and other health professionals including Internal Medicine Doctors, and trained healthcare professionals. Data will be collected across two visits, two to four weeks apart. At the first visit, each mine worker and supervisor at mining site will privately undergo a guided oral and structured questionnaire on demographic, socio-economic, and KAP related to silicosis and mining data will be collected. Each participant will be reassured and reminded that individual responses are confidential, inaccessible by the Wolfram Ltd. Company and will be anonymized prior to publication. Mine workers will also undergo an oral and structured questionnaire-based screening for silicosis symptoms. All subjects will then be assembled in small groups to receive targeted health education. At the second visit, mine workers and mining site supervisors will undergo structured interview for retention of health education by fulfilling a repeat KAP questionnaire, identical to the original. Data collected will include percentage of questions answered correctly, and will be further analyzed based on content areas. Mine workers who have worked in mining for at least one cumulative year will also undergo chest radiography and spirometry performed by trained clinical staff at Rwinkwavu District Hospital during their first visit with results interpreted by physician specialists. All questionnaire responses will be documented by data collectors and entered into a computerized database as the questionnaire is being performed. Data will be stored digitally on password-protected hard drives, tablets, and secure cloud servers.

The published sensitivity and specificity of the silicosis screening questionnaire will be reassessed in this study population by comparing the questionnaire results to chest radiography and spirometry findings from each subject.

Pilot Study

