Questionnaires and other study tools will be pre-tested in a pilot study conducted over the course of two days among 20 mine workers in Rwamagana District. We preferred to not use people under study area for avoiding any familiarity of tools before execution of the study which can be transmitted among miners which could tamper results. Feedback will be requested from these participants. Data collection and other tools will be adjusted and improved following the feedback and observations from the pilot study. In addition to sharpening the study methods, this pilot study will allow the study team to review pilot data to determine its accuracy and decide whether a retraining session will be necessary.

Data management, interpretation and analysis

All data of this study will be recorded and stored in REDCap before they will be exported into Stata v15.1 (Stata Corp, College Station, TX, USA) for analysis. Only the study team will have access to raw data and de-identified data will be kept in the analyzable dataset. We will use frequencies and percentages to summarize categorical data and median and interquartile ranges for continuous data. The pre-education KAP questionnaire responses will be compared to post-education responses and analyzed for statistically significant changes in KAP.

Institutionalized linkage to care and follow-up

For two years subsequent to this study, all mine workers who participate in this study along with local mine workers who do not participate will be provided with annual follow-up visits at Rwinkwavu District Hospital and those who were screened positive for silicosis will be seen every six months (or at internal medicine physicians discretion) depending on disease severity as an establishment of surveillance program for miners and Rwinkwavu District Hospital. Further program institutionalization will occur at the discretion of the Rwinkwavu District Hospital Director General and the Ministry of Health.

Expected Outcome

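### The KAP sample size treats one group of miners surveyed twice as two separate groups, so 186 and 224 count each person twice; the count should be restated, but recruitment need not change

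*Combined protocol and SAP*

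**What the plan says.** Under Study sample, the protocol takes a 50% starting proportion, 95% confidence, 0.8 power and a 20% difference from before to after. It arrives at a "required total sample size of 186 individuals (a minimum sample of 93 individuals will be required for the pre- and post-survey"). It then says that the requirement would "increase to 224 individuals (112 individuals in each survey) after accounting for a 20% non-response rate". The paragraph goes on: "We estimate our study sample to be around 995 mine workers, so we will have ample participants to conduct our study".

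Other sections describe who answers the two surveys. Study design calls it "a pre- and post-design to assess the silicosis-related knowledge, attitudes and practices (KAP) among mining workers before and after" the education programme. The recruitment section says: "Mine workers who accept to be a part of study, will avail him/herself two half days". Under Data collection, workers and site supervisors at the second visit "undergo structured interview for retention of health education by fulfilling a repeat KAP questionnaire, identical to the original".

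On the outcome, Data collection says: "Data collected will include percentage of questions answered correctly". On the analysis, the data management section says only: "The pre-education KAP questionnaire responses will be compared to post-education responses and analyzed for statistically significant changes in KAP".

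**The concern.** The design is one group measured twice, but the sample size is the kind used for two different groups. Two things follow.

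- The totals of 186 and 224 are numbers of questionnaires labelled as individuals. The quantity the design needs, the number of people who complete both visits, is never stated.
- The precision of a before-after comparison depends on how strongly a person's two answers are correlated, and the calculation has no place for that.

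The analysis section does not settle the matter. It names no test, does not say that the two questionnaires are linked by person, and gives no rule for people who miss the second visit, although Anticipated Problems expects some loss to follow-up. This is missing detail rather than a stated error, but it is why the corrected count should come with a matching analysis sentence.

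**Working it through.** **Inputs.** From Study sample: 50% before; a 20% difference, read as 50% to 70% because that reading reproduces the stated figure; 5% significance, taken as two-sided for the same reason; 80% power; 20% non-response; about 995 workers. The documents give no within-person correlation (rho), so values of 0, 0.3 and 0.5 are assumptions.

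**1. Reproducing the plan's figure.** The pooled formula for two independent proportions is

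n per group = [1.960 × √(2 × 0.6 × 0.4) + 0.842 × √(0.5 × 0.5 + 0.7 × 0.3)]² / 0.2² = 92.999, so 93.

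Then 2 × 93 = 186. Other versions do not match: 103 with continuity correction, 74 one-sided, 91 unpooled, 388 for a 20% relative rise (50% to 60%). The arcsine version also gives 93, but it too is for independent groups.

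**2. The allowance.** 93 × 1.2 = 111.6, so 112, and 2 × 112 = 224. Losing 20% of 112 leaves 112 × 0.8 = 89.6, fewer than 93. The correct inflation is 93 / 0.8 = 116.25, so 117 per survey.

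**3. The paired count.** For McNemar's test with difference d = 0.2,

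n = [1.960 × √pd + 0.842 × √(pd − d²)]² / d²,

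where pd is the share of people whose answer changes: pd = 0.5 × 0.3 + 0.7 × 0.5 − 2 × rho × √(0.25 × 0.21).

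| rho (assumed) | pd | n | People with both visits | Recruited if 20% do not return |
|---|---|---|---|---|
| 0 | 0.500 | 95.7 | 96 | 120 |
| 0.3 | 0.363 | 68.7 | 69 | 87 |
| 0.5 | 0.271 | 50.7 | 51 | 64 |

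The last column reads the 20% non-response as loss before the second visit. Set against it, 112 per survey is too few when rho is below about 0.07 and more than enough above that. The mathematical worst case, pd = 0.80, needs 155 people with both visits, or 155 / 0.8 = 193.75, so 194 recruited.

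**4. Against planned enrolment.** If all 995 joined and 20% did not return, 995 × 0.8 = 796 would complete both visits. That is an upper scenario, since no participation rate is given. It is 796 / 96 = 8.3 times the rho = 0 requirement.

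**5. If an unpaired test were run on these data.** Take 995 baseline answers, 796 returners and a true proportion of 50% with no change. The nominal variance is V = 0.25/995 + 0.25/796 (standard error 0.0238); the true variance is V − 2 × rho × 0.25/995. With no selective return the type I error is about 2.2% (rho 0.3) or 0.9% (rho 0.5). If returners and non-returners differ at baseline, the estimate shifts by 0.2 times the gap. At a 10-point gap the type I error is 9.6% or 6.7%; it passes 5% at gaps of about 6.4 points and just under 9 points respectively.

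**The case against.** The strongest reply is that nothing depends on these totals. The plan is to approach every worker, the brackets already show 93 and 112 per survey, and with no correlation to hand the two-group formula is a fair approximation: 93 pairs give about 79% power at zero correlation and about 91% at 0.3. Even 89.6 completers give about 77% and just under 90%. All of this stands, and it is why the point is minor. It does not make 186 or 224 the right count of individuals, nor 112 enough to leave 93.

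It is also fair that sizing on a proportion need not conflict with recording a percentage-correct score. Data collection does not say the score is the only measure, and categorical data are to be summarised as percentages, so item-level proportions are possible.

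Three stronger readings are tempting, and the documents do not support them:

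- **That the KAP comparison is underpowered.** Planned enrolment is several times any of the paired requirements above.
- **That an unpaired test is planned.** The analysis section names no test. A repeat questionnaire and research IDs (Ethical review and board approval) point towards linkage, although the form itself is an attachment not available here.
- **That leaving the test open is harmless because an unpaired test would be conservative.** That holds only with little or no selective return. Step 5 shows the error rate passing 5% at moderate baseline gaps.

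**Conclusion.** Minor, and wrong as written. The KAP sample size comes from a two-independent-group formula, its totals count each miner twice, and its 20% allowance leaves fewer than its own minimum. The brackets let a reader recover the per-survey numbers, and neither total sets enrolment.

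The independent-group origin of 93 is certain to rounding. The paired figures rest on an assumed correlation from 0 to 0.5 and on reading non-response as loss before the second visit. The conclusion that power is safe rests on enrolling most of about 995 workers; at zero correlation it would fail only if fewer than about 96 people completed both visits.

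All these figures treat workers as independent, although they come from nine sites and are taught in small groups. As a rough guide, with nine equal sites and an assumed intraclass correlation of 0.05 in the change, 796 completers are worth 796 / (1 + (796/9 − 1) × 0.05) = 148 independent people; at 0.10 they are worth 82. That limit applies equally to the plan's own calculation and is not caused by the double counting.

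**What to change.** In Study sample, replace 186 and 224 with a count of people who complete both visits, for example:

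> For a binary KAP item rising from 50% to 70% (two-sided 5%, 80% power), McNemar's test needs 96 people with both visits if the answers are uncorrelated, 69 at an assumed correlation of 0.3 and 51 at 0.5; if 20% do not return, 120, 87 or 64 are recruited. These figures ignore clustering by site and education group.

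In the analysis section, add a matching sentence:

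> The two questionnaires are linked by study ID and compared within person among those with both visits (McNemar's test for binary items; Wilcoxon signed-rank or paired t-test for the percentage-correct score). Baseline KAP of completers and non-completers is compared.

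The sponsor should choose the main KAP measure, and the test for it, before the data are seen.

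The cost is wording in two sections, with no added participants or visits. Research IDs are already planned; if the two forms do not carry them, one field per form is needed. The downside is that workers seen only at the first visit leave the main contrast, and pairing does not by itself remove selective drop-out, hence the comparison of completers with non-completers.

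### Education is given in small groups to workers surveyed twice, but the plan sizes KAP on independent samples and provides for neither pairing nor education session in the analysis

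*Combined protocol and SAP*

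**What the plan says.** All references are to the combined protocol and SAP.

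- **Delivery of education.** Data collection: "All subjects will then be assembled in small groups to receive targeted health education". The recruitment section places screening and education at each mine site in the afternoon. Study setting lists nine sites.
- **Measurement.** Data collection has the same workers complete an identical KAP questionnaire at a second visit two to four weeks later. Results are percent correct, with further analysis by content area.
- **Sizing.** Study sample takes a 50% baseline, 95% confidence and "a 0.8 power to detect a 20% difference from pre- to post-intervention". The result is that "a minimum sample of 93 individuals will be required for the pre- and post-survey", counted as 186 in total. This rises to "224 individuals (112 individuals in each survey) after accounting for a 20% non-response rate". No group size, ICC, design effect or pre-post correlation is given. The section expects about 995 workers.
- **Analysis.** Data management, interpretation and analysis says only: "The pre-education KAP questionnaire responses will be compared to post-education responses and analyzed for statistically significant changes in KAP". It names no test, variance estimator, pairing or grouping factor. No section mentions a session identifier.

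**The concern.** Workers taught together hear the same delivery and the same discussion, and they work at the same site. The Pilot Study section itself expects information to pass between miners: it pilots in another district so that familiarity with the tools does not spread and distort results. Similar sharing after teaching could make the changes of co-workers alike.

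If so, the average change carries less information than the count of workers suggests. A standard error that ignores session then misstates the precision of the Objective 3 result. Stable differences in baseline level between groups or sites cancel in within-worker change, so only correlation in the change itself matters.

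There is also a practical risk. If session membership is not recorded when the teaching happens, it may not be recoverable, and between-session variation could then not be estimated by any method.

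**Working it through.** **1. Reproduce the 93.** Inputs from Study sample: p1 = 0.50, p2 = 0.70, power 0.80 and 95% confidence, taken as two-sided 0.05. The pooled formula for two independent proportions is

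n = [1.96·√(2·0.6·0.4) + 0.842·√(0.25 + 0.21)]² / 0.20² = (1.358 + 0.571)² / 0.04 = 93.

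This is an exact match. Variants do not match: 74 one-sided, 91 with unpooled variance, 103 with continuity correction. The 93 therefore assumes two separate samples, independent workers and a design effect of 1. Counting 186 individuals in total fits the same reading, although each worker is surveyed twice.

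**2. A paired analysis that ignores session.** Group size m and the ICC of change are assumptions, because the documents give neither. DE = 1 + (m − 1)·ICC. The true interval is √DE times the reported one, and the actual two-sided error is 2·[1 − Φ(1.96/√DE)].

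| m | ICC | DE | Interval ratio | Actual error of a 5% test |
|---|---|---|---|---|
| 5 | 0.01 | 1.04 | 1.02 | 5.5% |
| 5 | 0.05 | 1.20 | 1.10 | 7.4% |
| 10 | 0.05 | 1.45 | 1.20 | 10.4% |
| 10 | 0.10 | 1.90 | 1.38 | 15.5% |
| 20 | 0.05 | 1.95 | 1.40 | 16.0% |
| 20 | 0.10 | 2.90 | 1.70 | 25.0% |

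For a given group size and ICC, these ratios do not shrink as more workers are enrolled.

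**3. An unpaired analysis, as the sizing formula implies.** The unpaired variance per worker is 0.25 + 0.21 = 0.46. With pre-post correlation ρ (assumed), the variance of the change is 0.46 − 2ρ·√(0.25·0.21) = 0.46 − 0.458ρ. Hence

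reported SE / true SE = √{0.46 / [(0.46 − 0.458ρ)·DE]}.

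| ρ | DE 1.45 | DE 1.95 |
|---|---|---|
| 0 | 0.83 | 0.72 |
| 0.3 | 0.99 | 0.86 |
| 0.5 | 1.17 | 1.01 |

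Below 1 the interval is too narrow, and above 1 it is too wide. The direction depends on ρ as well as on clustering.

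**4. Consequence at the planned scale.** Applying the plan's 20% non-response rate to 995 leaves 995 × 0.8 = 796. At ρ = 0, the least favourable case for non-negative ρ, the half-width for the change is 1.96·√(0.46/796) = 4.7 percentage points. At DE 2.90 it is 4.7 × 1.70 = 8.0 points. Both are well below the 20-point target.

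**5. Why 93 is not multiplied by DE here.** The ICC concerns a paired change, while the 93 is an unpaired figure. Pairing alone would lower it: a McNemar calculation for 0.50 against 0.70 needs 69 pairs at ρ = 0.3 and 51 at ρ = 0.5.

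**The case against.** A reader might infer that the plan tests the KAP change as if workers were independent. The documents do not say so. They name no test at all, and the independence assumption can be shown only for the sample size.

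A reader might also infer that the intervals will be too narrow and the false-positive rate will exceed 5%. That does not follow either. It holds for a paired analysis that ignores session when changes are positively correlated. If the analysis instead follows the unpaired sizing formula, step 3 shows that the two errors can cancel or reverse. This part of the objection stands in full. The cancellation would be accidental, however, and the plan controls neither error.

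A third inference is that the study is too small. It is not: the half-widths in step 4 leave a 20-point change clear throughout the assumed range.

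The magnitudes also rest on assumption. With groups of 5 and an ICC of 0.01 the effect is trivial. Even so, a large overall gain does not settle the matter, because results are also analysed by content area, where changes may be modest.

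Finally, near-complete enrolment might seem to make sampling error irrelevant. But the section on implications intends the findings to guide policy in Rwanda and elsewhere, so variation between sessions belongs in the uncertainty.

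**Conclusion.** The point holds as a gap in the plan that bears on the validity of intervals and p-values for Objective 3, not on power for the 20-point target. Three things are established: education is given in groups, the 93 ignores both pairing and clustering, and nothing in the plan would record session or use it.

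The size of the effect is conditional. For a paired analysis that ignores session, with assumed groups of 5 to 20 and an assumed ICC of change of 0.01 to 0.10, intervals should be 2% to 70% wider, and a nominal 5% test rejects about 5.5% to 25% of the time. For an unpaired analysis, the net error could go either way.

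This range covers correlation within sessions only. Correlation of change across a whole site could matter more: with 995/9 ≈ 111 workers per site and an assumed site ICC of 0.05, DE = 1 + 109.6 × 0.05 = 6.5. That is a reason to record site as well, not evidence that such correlation exists.

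**What to change.** 1. At the first visit, record an education-session ID and the site for each worker in REDCap, and link each worker's two questionnaires by study ID.
2. Specify the analysis as within-worker change in KAP score, overall and by content area, with standard errors clustered on session. In Stata this is a regression of the change with vce(cluster session). A mixed model or GEE with session as the cluster would also serve. Report the ICC of change with the result.
3. Beside the figure of 93, state that it assumes independent workers and ignores pairing.
4. If errors are also clustered on site as a sensitivity analysis, use a small-sample correction, because there are only nine sites.

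The cost is one extra REDCap field (site too, if it is not already captured), a few sentences in the plan and somewhat wider intervals than an analysis that ignores session. The result becomes a mean change from a model, because a simple signed-rank or McNemar test does not account for session. The medians and interquartile ranges already planned can stay as description. No further enrolment is needed. With groups of 5 to 20, 995 workers would form about 995/20 ≈ 50 to 995/5 = 199 sessions, enough for ordinary clustered errors.

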The study design will be cross-sectional study and is further detailed in Figure 4. There are three main objectives: silicosis prevalence; baseline silicosis-related knowledge, attitudes and practices (KAP); and the impact of occupational health education. A team of clinical and public health professionals affiliated with Partners In Health/Inshuti Mu Buzima and Rwinkwavu District Hospital will carry out the study with data collection assistance from trained fourth-year medical students from the University of Rwanda during their social medicine rotation. The preparation phase will involve contacting and establishing agreements with stakeholders from key organizations including Rwinkwavu District Hospital, Wolfram Mining and Processing Ltd., University of Rwanda and Partners in Health/Inshuti Mu Buzima. This phase will involve training medical student data collectors and recruiting study subjects. The study execution phase will firstly consist of a cross-sectional analysis of silicosis prevalence, adapting a validated silicosis questionnaire screening tool to the target study population and performing spirometry and chest radiography to all targeted miners [Suarthana, Eva, et al. "A Simple Diagnostic Model for Ruling Out Pneumoconiosis among Construction Workers." Occupational and Environmental Medicine, JSTOR]. This screening tool for ruling out occupational pneumoconioses, and silicosis specifically, was developed by researchers in the Netherlands. We will adapt and validate the use of this screening tool to Rwandan mine workers by comparing the screening results with objective spirometry and chest radiograph findings on all subjects who have spent at least one cumulative year working directly with mining products. Secondly, the execution phase will involve an analysis of existing silicosis-related KAP and the delivery of targeted occupational health education to study subjects followed by a reassessment of knowledge and attitudes. We will perform initial education program and KAP survey at the time of questionnaire based screening with re-assessment at 2-week time point. There are approximately 995 mine workers in the cachement are of this study and our goal is to try and involve all of these stakeholders. Baseline KAP survey will be done prior to our health education program on PPE, environmental

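### The plan contradicts itself on who is imaged and names no prevalence denominator; if only workers with a year or more are imaged, the result is not full-cohort prevalence

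*Combined protocol and SAP*

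**What the plan says.** Four statements bear on who receives radiography and spirometry.

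- Study design, on the cross-sectional phase: "performing spirometry and chest radiography to all targeted miners".
- Study design, on validating the screening tool: imaging is compared on "all subjects who have spent at least one cumulative year working directly with mining products".
- Data collection, on procedures: "Mine workers who have worked in mining for at least one cumulative year will also undergo chest radiography and spirometry".
- Data collection, on sensitivity and specificity: the tool is reassessed "by comparing the questionnaire results to chest radiography and spirometry findings from each subject".

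Two other sections fix the population. The recruitment section has a single list, introduced by "Inclusion criteria for all three study objectives, including silicosis screening, KAP assessment and education programs are". Under it a current worker qualifies by working at least weekly, with no minimum tenure. A minimum appears only on the route for former workers, "those who regularly worked in such mining operations for at least one cumulative year within the last 10 years". The Study sample section states the target: "Our goal is to sample the complete mining population so as to obtain accurate prevalence of the full cohort of miners", with an expected sample of about 995.

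The Data management, interpretation and analysis section plans frequencies and percentages. It names no analysis set for prevalence and does not say how enrolled workers without imaging are counted.

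**The concern.** Prevalence is Objective 1, and a prevalence has no meaning without its denominator. As written, a worker with six months of current weekly work is eligible for the prevalence objective and belongs to the stated target population, yet gets no radiograph or spirometry under the Data collection rule.

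Leaving such workers out is not neutral. The Background says that silicosis commonly takes years to become identifiable and that risk rises with cumulative silica exposure. Newer workers should therefore have less detectable disease than those imaged. A figure from the imaged group, presented as that of the whole workforce, would tend to be too high on this account. The plan intends its results to inform mining health policy, so the label matters.

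The tool-accuracy objective has the same defect: one sentence validates the questionnaire in those with a year or more, another in every participant.

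**Working it through.** **1. The plan's own figure.** The prevalence sample size of 189 reproduces as a one-sample test of 50% against 60%, two-sided 5% level, power 0.8, with the variance taken at the alternative: (1.960 + 0.842)² × 0.24 / 0.10² = 188.4, rounded up to 189. The point therefore does not rest on a sample-size error. Imaging 995 workers, or 696 if 30% were left out, far exceeds 189.

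**2. The imaging statements side by side.**

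| Section | Purpose | Who is imaged or compared |
|---|---|---|
| Study design | Cross-sectional phase | All targeted miners |
| Study design | Tool validation | A year or more, in direct work with mining products |
| Data collection | Procedures | A year or more, in mining generally |
| Data collection | Tool accuracy | Every subject |

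One might try to reconcile these by imaging everyone for prevalence and restricting only the tool validation. That fails, because the Data collection rule limits the imaging itself. It would also leave the last row in conflict with the second. The two one-year wordings differ too: under the general one, earlier mining elsewhere counts, so fewer workers would fall below the threshold.

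**3. Size of a mislabelled prevalence.** Let f be the share of the cohort with under one year, P1 the prevalence in those imaged and P0 the prevalence in those not imaged. Whole-cohort prevalence is (1 − f) × P1 + f × P0, so the overstatement is P1 minus this, which is f × (P1 − P0).

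Inputs: P1 = 30% to 50%, the planning range in the Study sample section. The documents give neither f nor P0; both are assumed.

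| f (assumed) | P0 = 0: P1 = 30% / 50% | P0 = 5%: P1 = 30% / 50% |
|---|---|---|
| 5% | 1.5 / 2.5 points | 1.25 / 2.25 points |
| 10% | 3.0 / 5.0 | 2.5 / 4.5 |
| 20% | 6.0 / 10.0 | 5.0 / 9.0 |
| 30% | 9.0 / 15.0 | 7.5 / 13.5 |

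In counts, with 995 workers and f = 10%, about 896 are imaged. At P1 = 30% that is 269 cases: 269/896 = 30.0%, but 269/995 = 27.0%. At P1 = 50% it is 448 cases: 448/896 = 50.0%, but 448/995 = 45.0%. The lower figures count unimaged workers as free of disease.

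**4. Against sampling error.** The nominal 95% half-width at n = 896 is 1.96 × √(0.21/896) = 3.0 points at 30%, and 1.96 × √(0.25/896) = 3.3 points at 50%. At an assumed 10% share, the labelling error is as large as the sampling error or larger, and more participants would not remove it.

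**The case against.** The strongest reply is that this is loose drafting. Both statements that mention tenure agree on one year, and the two unrestricted phrases could simply mean the people sent for imaging. The whole-population wording is a sampling goal, not a reporting label, and a percentage among those tested is the ordinary reading of the analysis section. Part of this stands: one clarification would settle who is imaged. But the text does not define the targeted group that way, and on that reading the stated whole-population prevalence still cannot be delivered, since workers under one year remain eligible for that objective.

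Three further limits are fair. The Study sample and recruitment sections contain no imaging rule; they supply the target and the eligibility that make the conflict matter. The one-year threshold for former workers is an eligibility criterion, not a third wording of the imaging rule. And the same inclusion list places former workers in all three objectives, so their place in Objective 1 is stated; what is not stated is whether the 995 includes them.

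A reader might take the 900 radiographs in the budget, against about 995 workers, as showing that 95 have under one year. The documents do not explain the gap, which could equally reflect expected participation or funds. It does not establish f.

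Figure 4, said to detail the design, and the attached questionnaire were not available to check, so the statement that no denominator is given applies to the body text.

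**Conclusion.** The point holds. Study design and Data collection each contradict themselves on who is imaged, and no prevalence denominator is stated. If the Data collection rule is followed, the study estimates prevalence and tool accuracy in imaged participants with a year or more of work, and not in the full cohort.

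Confidence is high in the contradiction and the missing denominator, not in the size. The 3.0 to 5.0 points rest on an assumed 10% share under one year, no disease in that group and the protocol's 30-50% range.

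A reader might infer that the study will overstate prevalence overall. The documents do not support that. The direction given concerns tenure only; the exclusion for "or other physical or medical disability that may limit involvement" could remove people with disease and push the measured figure down. No net direction is claimed. Nor should the two percentages in the worked count be read as bounds on workforce prevalence: they assume that everyone is enrolled, that only tenure prevents imaging, and that unimaged workers have either no disease or the same prevalence as those imaged.

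**What to change.** 1. Reconcile Study design and Data collection on who receives radiography and spirometry, with one wording of the one-year rule.
2. If imaging stays limited to a year or more, state the denominator for Objective 1 and for tool accuracy as imaged participants with at least that tenure. Put that group in place of the every-subject wording in Data collection, and replace the whole-cohort wording in Study sample.
3. Report numbers eligible, enrolled and imaged by tenure (under one year, one year or more) and by current or former worker. Say whether the 995 includes former workers.
4. Give any whole-workforce figure only as a sensitivity analysis with its assumptions stated. Cover everyone not imaged for any reason (tenure, refusal, missed visit, exclusion), and do not present it as a bound.

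The cost is protocol wording and one extra table, with no additional imaging. The downside is a narrower headline population.
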